#### C.5.1.3 Major Adverse Cardiovascular and Cerebrovascular Events

Major adverse cardiovascular and cerebrovascular events (MACCE) is defined as a composite of:

- All-cause death
- Myocardial infarction (MI)
- All stroke, and

- Reintervention (defined as any cardiac surgery or percutaneous reintervention catheter procedure that repairs, otherwise alters or adjusts, or replaces a previously implanted valve)

#### C.5.1.4 Major Adverse Event

Major adverse event (MAE) includes:

- MACCE
- Acute kidney Injury
- Cardiac tamponade
- Prosthetic valve dysfunction
- Cardiogenic shock
- Prosthetic valve endocarditis
- Life-threatening, disabling or major bleeding
- Major vascular complication
- Cardiac perforation
- Valve malpositioning

#### C.5.1.5 Adverse Device Effect (ADE) or Device-Related Adverse Event

An ADE is an adverse event related to the use of an investigational medical device. During this clinical investigation an event should be considered related to the device when it is the result of the Medtronic CoreValve™ System (MCS) and CoreValve™ Evolut™ R System:

- The transcatheter aortic valve (TAV)
- The delivery catheter system (DCS)
- The compression loading system (CLS/LS)
- The implant procedure

An event should be considered not related to the device when it is the result of:

- A pre-existing medical condition
- A new illness, injury or condition
- Medication

NOTE 1: This definition includes adverse events resulting from insufficient or inadequate instructions for use deployment, implantation, installation, or operation, or any malfunction of the investigational medical device.

NOTE 2: This definition includes any event resulting from use error or from intentional misuse of the investigational medical device.

#### C.5.1.6 Serious Adverse Device Effects (SADEs)

Adverse device effect that has resulted in any of the consequences characteristic of a Serious Adverse Event.

#### C.5.1.7 Unanticipated Adverse Device Effect (UADE)

An unanticipated adverse device effect or UADE is defined as “any serious adverse effect on health or safety or any life-threatening problem or death caused by, or associated with, a device, if that effect, problem, or death was not previously identified in nature, severity, or degree of incidence in the protocol or application (including a supplementary plan or application), or any other unanticipated serious problem associated with the device that relates to the rights, safety, or welfare of subjects” [21 CFR 812.3 (s)].

Those known adverse events related to the device, procedure or therapy are listed in Section O and in the Risk/Benefit Analysis section (Section D) of this document.

#### C.5.1.8 Unanticipated Serious Adverse Device Effect (USADE)

Serious adverse device effect which by its nature, incidence, severity or outcome has not been identified in the current version of the risk analysis report.

NOTE: Anticipated serious adverse device effect (ASADE) is an effect, which by its nature, incidence, severity or outcome has been identified in the risk analysis report.

#### C.5.1.9 Device Deficiency

Inadequacy of a medical device with respect to its identity, quality, durability, reliability, safety or performance.

NOTE: Device deficiencies include malfunctions, use errors, and inadequate labeling.

#### C.5.1.10 Technical Observation

A technical observation is a defect, malfunction, or failure of any part of the TAV or its components. This may pertain to the device or system not functioning according to its design intent. Each technical observation (whether or not associated with any untoward medical occurrence in a subject) will be reported on the Adverse Event (AE) eCRF and tabulated as an AE.

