#### C.5.1.1 Adverse Event

An adverse event (AE) is any untoward medical occurrence, unintended disease or injury, or untoward clinical signs (including abnormal laboratory findings) in subjects, users or other persons, whether or not related to the investigational medical device.

NOTE 1: This definition includes events related to the investigational medical device or the comparator.

NOTE 2: This definition includes events related to the procedures involved.

NOTE 3: For users or other persons, this definition is restricted to events related to investigational medical devices.

The following events in **Table 4** are expected to occur with any surgical implant and therefore should not be reported as AEs, unless they occur outside of the stated timeframe:

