#### C.5.2.4 Device Deficiencies and Technical Observations

Device Deficiency information and Technical Observations will be collected throughout the trial and reported to Medtronic.

Device Deficiencies and Technical Observations should be reported on an Adverse Event eCRF.

Device deficiencies that did not lead to an Adverse Event but could have led to an SADE:

- a) if either suitable action had not been taken,
- b) if intervention had not been made, or
- c) if circumstances had been less fortunate,

require immediate reporting (see **Table 6**). Initial reporting may be done on the eCRF completing as much information as is available. The original completed eCRF must be submitted to Medtronic as soon as possible.

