### TECHNICAL OBSERVATION

A defect, malfunction, or failure of any part of the Medtronic CoreValve™ System or CoreValve™ Evolut R System. This may pertain to the device or delivery and/or loading system not functioning according to its design intent.

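### C.5.1.10 counts every TAVI technical observation as an adverse event even when nothing happened to the patient, so all-AE counts by arm are not like-for-like

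*Combined protocol and SAP*

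**What the plan says.** C.5.1.1 sets the general definition: "An adverse event (AE) is any untoward medical occurrence, unintended disease or injury, or untoward clinical signs". A note adds that "This definition includes events related to the investigational medical device or the comparator", so the definition itself applies to both arms.

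C.5.1.10 then adds a rule for one class of record. It states: "A technical observation is a defect, malfunction, or failure of any part of the TAV or its components". On handling, it says: "Each technical observation (whether or not associated with any untoward medical occurrence in a subject) will be reported on the Adverse Event (AE) eCRF". The sentence runs on, so that the full instruction is that each observation "will be reported on the Adverse Event (AE) eCRF and tabulated as an AE". The glossary in O.2 has the same scope: "A defect, malfunction, or failure of any part of the Medtronic CoreValve™ System or CoreValve™ Evolut R System". It also names the delivery and loading systems. Neither definition mentions a surgical valve.

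C.5.1.9 defines a neighbouring class, the device deficiency, without tying it to the TAVI device: "Inadequacy of a medical device with respect to its identity, quality, durability, reliability, safety or performance". C.5.2.4 sends both classes to one form: "Device Deficiencies and Technical Observations should be reported on an Adverse Event eCRF". It does not say that deficiencies are tabulated as AEs, and it recognises deficiencies that led to no AE as a group of their own.

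**The concern.** The tabulation rule in C.5.1.10 conflicts with the definition in C.5.1.1. One section requires a medical occurrence; the other says that its absence makes no difference. A loading-system fault found before anything enters the patient, with the device replaced, is a technical observation under O.2. If the patient is unharmed it does not meet C.5.1.1, yet C.5.1.10 makes it an AE for that TAVI subject.

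The rule also reaches one arm only. Two kinds of table are exposed. An all-AE table by arm would carry rows for TAVI that have no tabulated equivalent for SAVR. A table of device-related AEs would combine device faults with patient harm, because C.5.1.5 builds the adverse device effect on the AE, and C.5.2 places device-related technical observations inside device-related AEs for reporting after 24 months. A reader of either table could not tell how much of the count is harm.

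**Working it through.** The plan states no rate of technical observations and no AE rate, so there is no figure to reproduce. The check is a comparison of the text, followed by an illustration of scale.

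**Text**

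1. *Is the medical occurrence required?* C.5.1.1: yes. C.5.1.10: expressly no. The two conflict for any observation without a medical consequence.
2. *Does the protocol keep the concepts apart elsewhere?* Yes. C.5.2 names AEs and technical observations as two things to be captured through 24 months, and C.5.2.4 separates deficiencies that led to no AE. The merger comes from the tabulation rule in C.5.1.10 and the post-24-month wording in C.5.2.
3. *Is the scope the same in both arms?* No. C.5.1.10 and O.2 cover the TAVI systems only. The immediate post-procedure list for TAVI (C.4.7.1) names technical observations; the list for SAVR (C.4.7.2) has only an AE review.
4. *Could a surgical-valve fault be recorded at all?* Yes, as a device deficiency under C.5.1.9, on the same AE eCRF under C.5.2.4. No sentence says it is then tabulated as an AE.
5. *Which planned outcomes does the rule touch?* The primary endpoint (C.6.5) is death or disabling stroke. MACCE (C.5.1.3), MAE (C.5.1.4) and early safety (C.6.8.1) are lists of named events. The labeling-claim list (C.6.10.1) has no any-AE outcome. Technical observation is a component of none of these, so the change to each from this rule is 0.

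**Scale (illustration only)**

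Inputs:
- TAVI arm: 1600 mITT subjects randomized 1:1 (C.6.5.2), so 1600 / 2 = 800, taken as approximate.
- q, the share of TAVI subjects with one harmless technical observation: assumed 1% to 10%.
- p, the share of TAVI subjects who have an AE anyway: assumed, shown at 0, 50% and 95%.

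Extra AE rows in TAVI = 800 × q. For q = 1%, 2%, 5% and 10% this gives 8, 16, 40 and 80. The rule adds 0 rows in SAVR.

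Rise in the share of TAVI subjects with any AE = (1 − p) × q, taking harmless observations as unrelated to whether the subject has another AE:

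| q | p = 0 | p = 50% | p = 95% |
|---|---|---|---|
| 1% | 1.0 points | 0.5 | 0.05 |
| 2% | 2.0 | 1.0 | 0.1 |
| 5% | 5.0 | 2.5 | 0.25 |
| 10% | 10.0 | 5.0 | 0.5 |

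The p = 0 column is a ceiling that would apply only if no TAVI subject had any other AE. Row counts do not depend on p, so they are affected more directly than the share of subjects with an event.

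**The case against.** The strongest reply is that no planned comparison is harmed. The text reviewed specifies no all-AE comparison between arms, and the outcomes that are compared are named clinical events. For the DSMB, C.5.4 names primary and safety-related secondary endpoints, serious AEs, deaths and whatever the board requests; it does not specify an all-AE table. A reader might infer that the safety comparison put before the DSMB and regulators is wrong by construction. The documents do not support that, because the layout of the AE tables is not shown. This part of the reply stands and limits the point to all-AE and device-related AE tabulations.

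A reader might also infer that SAVR has no counterpart at all. That goes too far: device deficiency is generic and uses the same form. What is missing is a tabulation rule for it.

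Third, some malfunctions already count. The anticipated adverse events in C.5.2.6, and the matching list in section D, include delivery-catheter malfunction that leads to re-crossing of the valve and a longer procedure, as well as frame fracture and malposition. The set of observations that only C.5.1.10 adds is therefore smaller than the full set of technical observations. This stands too, and is one reason why the size cannot be fixed.

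Finally, the rule is explicit, and over-counting against the investigational device is conservative. Both statements are true. They explain why the non-inferiority claim is not favoured, but they do not make a count of non-events an accurate AE count.

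**Conclusion.** The point holds as a contradiction between C.5.1.10 and C.5.1.1, with a one-sided effect on any all-AE tabulation by arm and a mixing of device performance with harm in device-related AE counts. It does not touch the primary endpoint, MACCE, MAE or any labeling-claim endpoint, and its direction is against TAVI.

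The size cannot be determined from the documents. The 8 to 80 extra rows rest on the assumed 1% to 10%, with one observation per affected subject. The rise of 0.05 to 0.5 points rests also on p = 95% and on the two kinds of event being unrelated. A reader who took the share of procedures with a fault as the rise in the any-AE share would be using the p = 0 ceiling, which the documents give no reason to adopt. The correction is worth making because the rule as written gives inaccurate counts and the repair is nearly free, not because any trial conclusion depends on it.

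**What to change.** In C.5.1.10, keep the capture on the AE eCRF. Replace the instruction to tabulate each observation as an AE with: *tabulated separately as a technical observation, and counted as an AE only if it meets the definition in C.5.1.1*. Bring the post-24-month wording in C.5.2 into line, so that device-related technical observations are reported beside device-related AEs and not inside them.

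C.5.2.4 needs no correction of a tabulation rule, since it does not class deficiencies as AEs. Add one statement there that deficiencies of the surgical valve, which can already be recorded under C.5.1.9 and C.5.2.4, are tabulated by the same rule as technical observations.

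The cost is one derived flag, showing whether the record meets C.5.1.1, and one extra table. No data are lost, and no endpoint or sample size changes.

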### *C.5.2 Reporting*

Investigators are required to keep records on “all relevant observations, including records concerning adverse device effects (whether anticipated or unanticipated)” [21 CFR 812.140; ISO 14155 (2011)]. Adverse event collection will begin from the point of trial enrollment to trial closure. All new or worsening (from baseline) adverse events and technical observations will be captured on the AE eCRF through the 24-month follow-up visit. It is the responsibility of the Investigator to assess the subject for adverse events and capture the required adverse event information on the AE eCRF.

Once a subject has completed their 24-month scheduled follow-up visit only serious adverse events, major adverse events, cardiovascular events, device-related adverse events, including device related technical observations, unanticipated adverse device effects (UADE) or unanticipated serious adverse device effects (USADE), all strokes (CVAs) and deaths will be required to be reported. Reference section C.5.1 Adverse Events for event definitions and criteria. Medtronic representatives or their designees will conduct monitoring visits to review source documentation and verify the complete and accurate capturing of adverse events.

The Investigator must also notify the responsible IRB/MEC regarding new and significant safety information and any event identified by Medtronic that requires expedited FDA, and/or local regulatory agency, reporting as serious, unexpected, and related to the investigational device. It is the responsibility of the investigator to ensure site specific IRB/MEC safety reporting requirements are met.

Medtronic Clinical will ensure all device-related adverse events and all procedure-related SAEs are processed according to internal policies and procedures. When necessary, Medtronic Field Assurance will respond to sites in writing with the findings related to the product experiences.

The general procedure for investigators reporting any adverse event is as follows:

- Report the event to Medtronic as soon as possible but no later than the timeframes outlined below. (At the time of Site Initiation, sites will be provided with the telephone and other applicable contact information of the appropriate Medtronic designee).
- Complete all sections of the Adverse Event eCRF.
- Each unique event/diagnosis must be documented separately.
- Documented pre-existing conditions are not considered to be reportable AEs unless there is a change in the nature or severity of the condition.
- The Adverse Event eCRF must be reviewed by the Investigator.

Reporting guidelines related to specific types of adverse events are outlined below.

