  -  All subjects should have screening thoracic and abdominal CT angiograms with complete visualization of both iliacs, femorals, and aorta (and subclavian/axillaries, if applicable), up to and including the aortic annulus
  -  In addition to the protocol required assessment (NIHSS and MMSE); for subjects with neurological event or stroke, additional NIHSS and MMSE exams are to be performed at 30 days and 90 days post-event. mRS should be completed at 7 days post-event or discharge (whichever occurs first), 30 days, and 90 days post-event. NIHSS is also to be done within 24 hours of any aortic valve or ascending aortic intervention
  -  NIHSS to be done within 24 hours post- procedure
  -  Additional Neurological Assessments include: Visual Fields Testing, Gait Assessment, Hand Function, Writing Evaluation, and Drawing Assessment
  -  SAE, MAE, cardiovascular events, device-related events, including device-related technical observations, UADEs, USADEs, all stroke (CVAs), and death reports
  -  Use of relevant medications (diuretics, aspirin, anticoagulants, ACE-I, ARB, beta-blockers, statins and anti-platelets)
  -  Quality of Life Questionnaires collected at baseline may be administered any time after the subject has provided informed consent but should be collected prior to informing the subject of randomization assignment
  -  Quality of Life Questionnaire – EQ-5D to be administered via telephone. SF-36 will also be collected in selected geographies, refer to **Appendix R.12**

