- Valve-related dysfunction requiring repeat procedure (BAV, TAVI, or SAVR)
- All-cause death

Early safety composite endpoint-incidence estimates will be provided for the two treatment groups at 30 days. The statistical method will be the Bayesian version of a comparison of proportions.

5. Incidence of Clinical Efficacy (after 30 days) at 6 months, 12 months, 18 months, 24 months and annually thereafter up to 5 years. Clinical efficacy defined as a composite of:
- All-cause mortality
  - All stroke (disabling and non-disabling)
  - Requiring hospitalizations for valve-related symptoms or worsening congestive heart failure
  - NYHA class III or IV
  - Valve-related dysfunction (mean aortic valve gradient  $\geq 20$  mmHg, EOA  $\leq 0.9$ - $1.1$   $\text{cm}^2$  and/or DVI  $< 0.35$  m/s, AND/OR moderate or severe prosthetic valve regurgitation\*)

Clinical efficacy estimates will be provided for the two treatment groups at 6 months, 12 months, 18 months, 24 months and annually thereafter up to 5 years. The statistical method will be the Bayesian version of a comparison of proportions (with predictions).

\*Refers to VARC-2 definitions

6. Incidence of Time-Related Safety at 30 days, 6 months, 12 months, 18 months, 24 months and annually thereafter up to 5 years. Time-Related Safety defined as a composite of:
- Structural valve deterioration:
    - Valve-related dysfunction (mean aortic valve gradient  $\geq 20$  mmHg, EOA  $\leq 0.9$ - $1.1$   $\text{cm}^2$  and/or DVI  $< 0.35$  m/s, AND/OR moderate or severe prosthetic valve regurgitation\*)
    - Requiring repeat procedure (TAVI or SAVR)
  - Prosthetic valve endocarditis
  - Prosthetic valve thrombosis
  - Thromboembolic events (eg. stroke)
  - VARC bleeding, unless clearly unrelated to valve therapy (eg. trauma)

Time related safety composite endpoint-incidence estimates will be provided for the two treatment groups at 30 days, 6 months, 12 months, 18 months, 24 months and annually thereafter up to 5 years. The statistical method will be the Bayesian version of a comparison of proportions (with predictions).

\*Refers to VARC-2 definitions

7. Conduction disturbance requiring permanent pacemaker implantation at 30 days, 6 months, 12 months, 18 months, 24 months, and annually thereafter up to 5 years.

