12. Echocardiographic assessment of prosthetic valve performance at discharge, 6 months, 12 months, 24 months, and annually thereafter up to 5 years using the following measures:

- transvalvular mean gradient
- effective orifice area
- degree of prosthetic aortic valve regurgitation (including transvalvular and paravalvular)

The four echocardiographic measurements will be evaluated at discharge, 6 months, 12 months, 24 months, and annually thereafter up to 5 years. All implanted subjects undergoing echocardiography procedures will be evaluated.

Continuous measures will be evaluated using a Bayesian version of a two-sample t-test. Categorical variables will be evaluated using Bayesian version of a comparison of polytomous outcomes.

Additionally, incidence of moderate/severe aortic insufficiency at discharge will be compared between groups using the Bayesian version of a comparison of proportions.

13. Aortic valve disease related hospitalizations

The number of subjects re-hospitalized after the initial index procedure will be compared at 30 days, 6 months, 12 months, 18 months, 24 months, and annually thereafter up to 5 years.

Incidence of recurrent hospitalization will be provided at 30 days, 6 months, 12 months, 18 months, 24 months, and annually thereafter up to 5 years. The statistical method will be the Bayesian version of a comparison of proportions (with predictions).

14. Cardiovascular deaths and valve-related deaths

The number of subjects experiencing cardiovascular deaths and valve-related deaths at 30 days, 6 months, 12 months, 18 months, 24 months, and annually thereafter up to 5 years. Incidences will be compared between groups. The statistical method will be the Bayesian version of a comparison of proportions (with predictions).

15. Strokes and TIAs

The number of subjects with strokes (of any severity) and TIAs at 30 days, 6 months, 12 months, 18 months, 24 months, and annually thereafter up to 5 years. A separate analysis will be performed for each of the following:

- a composite of all strokes and TIAs
- disabling strokes only
- non-disabling strokes only
- TIAs only

The statistical method will be the Bayesian version of a comparison of proportions (with predictions).

Additionally, incidence of all strokes at 30 days or hospital discharge, whichever is longer, will be compared between groups using the Bayesian version of a comparison of proportions.

16. Peri-procedural Neurological Injury (Stroke, TIA, Encephalopathy)

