## BLEEDING EVENT

Bleeding event will be defined according to the Valve Academic Research Consortium (VARC)-2; Updated Standardized Endpoint Definitions for Transcatheter Aortic Valve Implantation (TAVI); 2012-10-09.

Life-threatening or Disabling Bleeding

 
• Fatal bleeding (BARC type 5) OR
 
• Bleeding in a critical area or organ, such as intracranial, intraspinal, intraocular, or pericardial necessitating pericardiocentesis, or intramuscular with compartment syndrome (BARC type 3b) OR
 
• Bleeding causing hypovolemic shock or severe hypotension requiring vasopressors or surgery OR
 
• Overt source of bleeding with drop in hemoglobin of <math>\geq 5</math> g/dL or whole blood or packed red blood cells (RBC) transfusion <math>\geq 4</math> units* (BARC type 3b)
 

Major Bleeding ( BARC type 3a )

 
• Overt bleeding either associated with a drop in the hemoglobin level of at least 3.0g/dL or requiring transfusion of 2-3 units of whole blood/RBC, or causing hospitalization or permanent injury or requiring surgery AND
 
• Does not meet criteria of life-threatening or disabling bleeding
 

Minor Bleeding ( BARC type 2 or 3a, depending on severity )

 
• Any bleeding worthy of clinical mention (eg. access site hematoma) that does not qualify as life-threatening, disabling or major
 

\* Given one unit of packed RBC typically will raise blood hemoglobin concentration by 1g/dL, an estimated decrease in hemoglobin will be calculated.  
BARC = Bleeding Academic Research Consortium

Life-threatening and Major bleeding events are considered to be serious.

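### After the 24-month visit sites are not clearly required to report minor bleeding, and possibly TIA, although endpoints containing them are compared annually to 5 years

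*Combined protocol and SAP*

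**What the plan says.** **Up to 24 months.** C.5.2 is complete: "All new or worsening (from baseline) adverse events and technical observations will be captured on the AE eCRF through the 24-month follow-up visit".

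**After 24 months.** C.5.2 continues: "Once a subject has completed their 24-month scheduled follow-up visit only serious adverse events, major adverse events, cardiovascular events, device-related adverse events", followed by unanticipated device effects, all strokes and deaths. Footnote 10 of Table 3, which governs the 3- to 5-year visits, repeats the list: "SAE, MAE, cardiovascular events, device-related events, including device-related technical observations, UADEs, USADEs, all stroke (CVAs), and death reports". Neither place names TIA or minor bleeding.

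**Endpoints that run to 5 years.** In C.6.8.1, endpoint 6 (Time-Related Safety) has as one component "VARC bleeding, unless clearly unrelated to valve therapy (eg. trauma"; no severity floor is given. Section O.2 defines VARC-2 bleeding with a minor category: "Any bleeding worthy of clinical mention (eg. access site hematoma) that does not qualify as life-threatening, disabling or major". Endpoint 15 covers "The number of subjects with strokes (of any severity) and TIAs at 30 days, 6 months, 12 months, 18 months, 24 months, and annually thereafter", with separate analyses of TIAs alone and of strokes and TIAs together.

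**Device-related.** C.5.1.5 states that "an event should be considered related to the device when it is the result of the Medtronic CoreValve" or Evolut R system, including the implant procedure. It gives no counterpart for a surgical valve.

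**The concern.** An incidence comparison needs the same events to be collected over the whole period being compared. Here the collection rule changes at each subject's 24-month visit, while the definition of endpoint 6 does not. A subject whose first qualifying event is a minor bleed at, say, month 40 meets the endpoint but need not appear in the data. The 3-, 4- and 5-year incidences would then mix two ascertainment rules, and part of any slowing after month 24 could come from reporting rather than risk.

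Two related questions follow: whether TIA suffers the same loss, and whether the one category tied to the investigational device makes late capture differ between arms. At stake are the long-term secondary comparisons.

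**Working it through.** The plan states no figure on this point, so the check is a reconciliation of its sections.

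**1. Minor bleeding against each retained category**

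- *Serious adverse event (C.5.1.2):* the additional default list includes life-threatening and major bleeding, not minor. A bleed that causes hospitalization is already major under O.2, so a minor bleed will seldom qualify.
- *Major adverse event (C.5.1.4):* life-threatening, disabling or major bleeding only.
- *Stroke or death:* not applicable.
- *Cardiovascular event:* undefined. Some sites might include a vascular bleed; nothing tells them to.
- *Device-related (C.5.1.5):* TAVI only, and events resulting from medication are excluded.

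Minor bleeding therefore has no clear reporting route in either arm.

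**2. TIA against the same list**

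- It is absent from MACCE (C.5.1.3), from major adverse events and from the default serious events. It is serious if it leads to admission.
- The stroke entry does not cover it: exclusion criterion 10 and O.2 both separate TIA from stroke.
- *Cardiovascular events* may cover it. C.5.2 refers to C.5.1 for definitions, but neither C.5.1 nor O.2 defines the term. O.2 places deaths from neurological events under cardiovascular mortality, which favors inclusion. The MACCE title separates cardiovascular from cerebrovascular, which favors exclusion.

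The status of a TIA without admission is ambiguous.

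**3. Other sources in years 3 to 5**

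C.4.9.7 schedules NIHSS as the only neurological test, and its adverse event review refers back to C.5.2. In Table 3 routine laboratory tests end at 30 days and concomitant medications at 24 months. An annual NIHSS will usually miss a deficit that lasts under 24 hours. The adverse event report is thus the main source for both event types.

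**4. Symmetry between arms**

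Major adverse events stay reportable in both arms without a seriousness test. They include prosthetic valve dysfunction, prosthetic valve endocarditis, malpositioning and, through MACCE, reintervention. O.2 lists valve thrombosis among the failure modes of dysfunction. Only a non-serious, valve-attributed event outside the major adverse event and cardiovascular categories is reportable in TAVI and not in SAVR.

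**5. Illustration of scale (assumptions, not plan figures)**

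Let *h* be a constant annual first-event rate, equal in both arms, and *f* the share of events not reportable after 24 months. Deaths are ignored.

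- True 5-year incidence: 1 − exp(−5h)
- Observed: 1 − exp(−2h − 3h(1 − f))

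| h | f | True | Observed | Relative loss |
|---|---|---|---|---|
| 1% | 25% | 4.88% | 4.16% | 15% |
| 1% | 80% | 4.88% | 2.57% | 47% |
| 3% | 25% | 13.93% | 11.97% | 14% |
| 3% | 80% | 13.93% | 7.50% | 46% |

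For example, h = 1% and f = 25% give 1 − exp(−0.02 − 0.0225) = 4.16%.

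If TAVI keeps a share *d* of the otherwise unreportable events as device-related, *f* becomes f(1 − d) in that arm. With d = 0 the arms lose equally. With d = 30% to 60% and the values above, TAVI would appear higher by 0.2 points (h = 1%, f = 25%, d = 30%) to 3.9 points (h = 3%, f = 80%, d = 60%), although the true rates are equal.

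**The case against.** The strongest reply is that little is lost. Events up to 24 months are fully captured, and each endpoint counts a subject once. Any bleed that causes admission, needs surgery, is transfused with 2 or 3 units, or lowers hemoglobin by at least 3 g/dL is at least major and stays reportable. Endpoint 6 also drops bleeding clearly unrelated to valve therapy. All of this stands, and it confines the loss to subjects whose first qualifying event is late, minor and unreported. It does not remove it.

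A reader might infer three stronger things that the documents do not support.

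- *That TIA is excluded after 24 months.* Naming strokes separately does not show that cerebrovascular events fall outside *cardiovascular events*, because the list is redundant: strokes and deaths are already major adverse events through MACCE. C.4.11 also asks for extra NIHSS examinations after a TIA with no 24-month limit. The term is undefined, not exclusionary.
- *That device-related is the only route left for non-serious valve events, so the late comparison is biased by arm.* The major adverse event category keeps most valve events in both arms, and a late bleed attributed to medication is not device-related in TAVI either. The asymmetry is real but narrow.
- *That a definite share of subjects is missed.* Taking 1%, 3% or 5% per year and 1 − exp(−3r) gives 3.0%, 8.6% and 13.9%. Those rates are assumed, the sum pools events from two different endpoints, and it supposes that none is reported.

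Operational definitions could also sit in the case report forms, which are provided under separate cover, or in the events committee charter. That is a reason to check them, but C.5.2 is the instruction that sites follow.

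**Conclusion.** The mismatch holds for minor bleeding. Endpoint 6 counts it to 5 years, while C.5.2 and Table 3 footnote 10 stop clearly requiring it after the 24-month visit. The 3- to 5-year incidence of Time-Related Safety may be undercounted; the text does not establish that it will be. For TIA the finding is an ambiguity that turns on one undefined term: if that term includes TIA, there is no loss for endpoint 15. The difference between arms is confined to residual non-serious valve-attributed events and, where it operates, would make TAVI look worse.

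The size is unknown, because the documents give no rate for minor bleeding or TIA and no reportable share. The tabulated losses of about 14% to 47% rest wholly on the assumed *h* and *f*.

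The consequence is limited. The primary endpoint is assessed at 24 months. Every test in the labeling hierarchy of C.6.10 is at or before 24 months, and none uses TIA or Time-Related Safety. The point concerns the credibility of long-term secondary results and is worth correcting because the correction is cheap.

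**What to change.** **Preferred.** In C.5.2 and Table 3 footnote 10:

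- name TIA and all VARC-2 bleeding, of any severity, as reportable after 24 months in both arms;
- make the device-related category cover either trial valve, transcatheter or surgical;
- define *cardiovascular events* in C.5.1 or O.2, so that sites read it alike.

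The adverse event form and the annual review already exist. The cost is a short amendment, site guidance and modest extra event entry in years 3 to 5. Late events not recorded at the time may be hard to recover, so the change is better made early.

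**Alternative, if collection is not to be extended.** After 24 months, restrict the bleeding component of endpoint 6 to life-threatening, disabling or major bleeding. Report TIA beyond 24 months only if it is confirmed to be a reportable cardiovascular event. The cost is a narrower late safety composite and possibly the loss of the late TIA analyses.
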